16.1.1. ALL TEAES

Incidence of TEAEs will be presented by System Organ Class (SOC) and Preferred Term (PT) and broken down further by maximum severity and relationship to study medication.

16.1.1.1.Severity

Severity is classed as mild/ moderate/ severe (increasing severity). TEAEs starting after the first dose of study medication with a missing severity will be classified as severe. If a subject reports a TEAE more than once within that SOC/ PT, the AE with the worst case severity will be used in the corresponding severity summaries.

16.1.1.2. Relationship to Study Medication

Relationship, as indicated by the Investigator, is classed as "Unrelated", "Unlikely", "Possibly", "Probably" and "Definitely" (increasing severity of relationship). Missing relationship will be classified as related. If a subject reports the same AE more than once within that SOC/ PT, the AE with the worst case relationship to study medication will be used in the corresponding relationship summaries.

A list of TEAEs will be presented.

16.1.2. SERIOUS TREATMENT EMERGENT ADVERSE EVENTS

Serious Treatment Emergent Adverse Events (SAEs) are those events recorded as "Serious" on the Adverse

Document: 2014-000674-18 Statistical Analysis Plan Version 7.0 Version Number: 7.0

Version Date:

13JAN2020

Template No.: CS_TP_BS016 Revision 5 Reference: CS_WI_BS005

Effective Date: 01Apr2018

Author:

Events page of the (e)CRF. A summary of serious TEAEs by SOC and PT will be prepared. A list of Serious TEAEs will be presented.

16.1.3. TREATMENT EMERGENT ADVERSE EVENTS LEADING TO DEATH

TEAEs leading to Death are those events which are recorded as "Fatal" on the Adverse Events page of the (e)CRF. A summary of TEAEs leading to death by SOC and PT will be prepared.

A list of TEAEs leading to death will be presented.

16.1.4. ALL ADVERSE EVENTS LEADING TO DEATH

AEs leading to Death are those events which are recorded as "Fatal" on the Adverse Events page of the (e)CRF. A summary of AEs leading to death and discontinuation by SOC and PT will be presented. A list of All AEs leading to death will be presented.

16.2. LABORATORY EVALUATIONS

Results from the central laboratory will be included in the reporting of this study by laboratory parameter. Presentations will use SI Units.

The following summaries will be provided for laboratory data:

- Actual and change from baseline by visit (for quantitative measurements)
- Incidence of markedly abnormal values according to central laboratory reference ranges
- Shift from baseline according to normal range criteria (for quantitative measurements and categorical measurements)
- Listing of values meeting markedly abnormal criteria

Sample collection information will be listed. Lab results will be listed for Hematology, Chemistry and Urinalysis respectively. Lab results which are out of normal range, or meet the markedly abnormal, will also be listed respectively for Hematology, Chemistry and Urinalysis.

Number and percentage of subjects with elevated creatinine will be summarized by visit.

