8. Subjects may be renal transplant patients if time post-transplant has been greater than 6 months prior to Screening, with stable graft function (and eGFR ≥ 30 mL/min/1.73 m²) for at least 6 months, stable use of immunosuppressive therapy for at least 30 days prior to Screening, and documented evidence that there is no transplant renal artery stenosis.
9. All female subjects who are of child bearing potential* (defined as females aged ≥ 12 years old and younger females who, at the discretion of the investigator, are deemed to be of reproductive potential) who are sexually active agree to routinely use adequate contraception* from Screening until the last dose of study medication. All female subjects aged ≥ 12 years old and younger females who, at the discretion of the investigator, are deemed to be of reproductive potential must provide a negative serum pregnancy test at Screening and a negative urine pregnancy test at Day 1.

*Definitions and acceptable methods of contraception are defined in [Section 9.1.9](#)
Contraception and Pregnancy Avoidance Procedure and reporting responsibilities are
defined in [Section 9.1.10](#) Pregnancy.

10. The subject is untreated, or willing, and in the opinion of their treating physician, can safely be withdrawn from previous antihypertensive medications for a maximum of 4 weeks (if a washout extension is required) prior to randomization.
11. The subject has clinical laboratory results (including clinical chemistry, hematology, and complete urinalysis) within the reference range for the testing central laboratory unless the results are deemed by the investigator to be stable and related to the subject's medical history and/or not clinically significant, with the exception of hyperkalemia or pertinent electrolyte disorders (exclusion criterion 16). Subjects with LFTs under the values specified by exclusion criterion 15 may be included provided the subject does meet the other criteria stated in that exclusion (i.e. active liver disease, jaundice and severe hepatic impairment),

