For each laboratory parameter, at each scheduled time point over the course of the study (eg, at each visit), the following will be displayed for the absolute values and for the change from Baseline values: number of subjects, mean, SD, minimum, median, maximum. Markedly abnormal laboratory values will be tabulated (n and %). The number and percent of subjects with marked abnormality in each of the laboratory parameters will be presented. In addition, shift tables will be presented showing the number of subjects with low, normal, or high values according to the central laboratory reference ranges at Baseline and at the scheduled time points. The number of subjects in each of the combinations of shifts will be presented. Laboratory data collected more than 7 days after the last dose of study medication will be excluded from the summaries but will be listed. A listing of all laboratory data will be provided.

The other safety variables will be summarized by descriptive statistics (eg, number of subjects, mean, SD, median, minimum and maximum values, and the number and percentage of subjects in specified categories).

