16.2.1. LABORATORY REFERENCE RANGES AND MARKEDLY ABNORMAL CRITERIA

Quantitative laboratory measurements will be compared with the relevant laboratory reference ranges in SI units and categorized as:

- Low: Below the lower limit of the laboratory reference range.
- Normal: Within the laboratory reference range (upper and lower limit included).
- High: Above the upper limit of the laboratory reference range.

Document: 2014-000674-18 Statistical Analysis Plan Version 7.0 Version Number: 7.0

Author: Version Date: 13JAN2020

Template No.: CS_TP_BS016 Revision 5 Reference: CS_WI_BS005

Effective Date: 01Apr2018

In addition to the high and low quantitative laboratory assignments (as identified by means of the laboratory reference ranges), markedly abnormal quantitative safety (and other) laboratory assessments will also be identified in accordance with the predefined markedly abnormal criteria as presented in provided in Appendix 3.

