APPENDIX 3. MARKEDLY ABNORMAL CRITERIA

LAB CATEGORY	LAB NAME	SEX	LOW CRITERIA	HIGH CRITERIA	DERIVED CRITERIA LOW (USE FOR OUTPUTS)	DERIVED CRITERIA HIGH (USE FOR OUTPUTS)
Hematology	Hemoglobin	M/F	< Baseline – 3 g/dL		<baseline -="" 30="" g="" l<="" td="">	</baseline>	
Hematology	Hematocrit	M/F	< 0.8 x Baseline		<0.8 x Baseline	
Hematology	RBC count	M/F	< 0.8 x Baseline		<0.8 x Baseline	

2014-000674-18 Statistical Analysis Plan Version 7.0 Document: Version Number: Author: Version Date: 13JAN2020

Template No.: CS_TP_BS016 Revision 5 Reference: CS_WI_BS005

Effective Date: 01Apr2018

		l .		> 20 x		I .
Hematology	WBC count	M/F	< 2 x 103/mm3	103/mm3	<2 x 10^9/L	>20 x 10^9/L
Hematology	Platelet count	M/F	< 50 x 103/mm3	> 700 x 103/mm3	<50 x 10^9/L	>700 x 10^9/L
Chemistry	ALT	M/F		>3x ULN		>3 x ULN
Chemistry	AST	M/F		>3x ULN		>3 x ULN
Chemistry	GGT	M/F		>3x ULN		>3 x ULN
Chemistry	Alkaline phosphatase	M/F		>3x ULN		>3 x ULN
Chemistry	Total bilirubin	M/F		>2.0x ULN		>2.0 x ULN
Chemistry	Albumin	M/F	<2.5 g/dL		<25 g/L	
Chemistry	Total protein	M/F	<0.8x LLN	>1.2x ULN	<0.8 x LLN	>1.2 x ULN
Chemistry	Creatinine	M/F		>1.5 x Baseline		>1.5 x Baseline
Chemistry	Sodium	M/F	<130 mEq/L	>150 mEq/L	<130 mmol/L	>150 mmol/L
Chemistry	Potassium	M/F	<3.0 mEq/L	>6.0 mEq/L	<3.0 mmol/L	>6.0 mmol/L
Chemistry	Blood Urea Nitrogen	M/F		>3x ULN		>3 x ULN
Chemistry	Calcium	M/F	<0.8x LLN	>1.2x ULN	<0.8 x LLN	>1.2 x ULN
Chemistry	Creatine kinase	M/F		>10x ULN		>10 x ULN
Chemistry	Uric Acid	М		>10.5 mg/dL		>625 umol/L
Chemistry	Uric Acid	F		>8.5 mg/dL		>506 umol/L
Urinalysis	Blood	M/F		≥1+		>=1+
Urinalysis	Glucose	M/F		≥1+		>=1+
Urinalysis	Ketones	M/F		≥2+		>=2+
Urinalysis	Casts	M/F		Any		Any
Urinalysis	Casts	M/F		Any		Any
Urinalysis	Microscopic RBCs*	M/F		≥5/hpf		>=5/hpf
Urinalysis	Microscopic RBCs*	M/F		≥5/hpf		>=5/hpf
Urinalysis	Microscopic WBC	M/F		≥20/hpf		>=20/hpf
Urinalysis	рН	M/F	<=4	>=8	<=4	>=8

Document: 2014-000674-18 Statistical Analysis Plan Version 7.0 Version Number: 7.0

Author: Version Date: 13JAN2020

Template No.: CS_TP_BS016 Revision 5 Reference: CS_WI_BS005

Effective Date: 01Apr2018

7.0

Statistical Analysis Plan

Urinalysis	Protein	M/F		>=1+		>=1+
	Specific					
Urinalysis	Gravity	M/F	<1.005		<1.005	

Document: 2014-000674-18 Statistical Analysis Plan Version 7.0 Version Number: Author: Version Date: 13JAN2020

Template No.: CS_TP_BS016 Revision 5 Reference: CS_WI_BS005

Effective Date: 01Apr2018

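### The table of markedly abnormal laboratory values does not separate urinalysis findings already present at baseline from new ones

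*SAP*

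**What the plan says.** - **The table.** SAP 16.2 lists, among the laboratory summaries, "Incidence of markedly abnormal values according to central laboratory reference ranges". SAP 16.2.1 has markedly abnormal values identified "in accordance with the predefined markedly abnormal criteria" given in Appendix 3. The two sections therefore name different sources for the limits. Protocol 13.1.5 asks for the number and percentage of subjects with a marked abnormality in each parameter.
- **The limits.** In SAP Appendix 3 the urinalysis limits are absolute: protein, blood and glucose ≥1+, ketones ≥2+, any casts, red cells ≥5/hpf, white cells ≥20/hpf. Creatinine is judged against the child's own starting value (">1.5 x Baseline"), as are hemoglobin, hematocrit and red cell count.
- **Who may enter.** Protocol 7.1, criterion 11, requires laboratory results, including urinalysis, to be in range "unless the results are deemed by the investigator to be stable and related" to medical history, and/or not clinically significant. Protocol 6.2.1 anticipates many children with underlying chronic kidney disease (CKD) and targets at least 20% secondary hypertension. Renal transplant recipients are eligible under criterion 8.
- **Other baseline-aware output.** The same SAP 16.2 list plans shift tables from baseline by normal range, for categorical as well as quantitative results, and listings.

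**The concern.** A table described as an incidence will be read as events arising on treatment. Under the rule as written, a child with CKD who has 2+ protein on Day 1 and is unchanged at Weeks 6, 8 and 52 meets the protein criterion in the DB, Withdrawal and OL phases, because SAP 16 summarizes safety by phase. Two consequences follow.

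- **OL phase.** There is no randomized comparator, so the printed rate stands alone. Stable renal disease would add to an apparent rate of proteinuria or hematuria on azilsartan medoxomil (AZM).
- **DB phase.** The same children add a roughly equal background to every arm. This pulls a ratio of rates toward 1 and makes a genuine excess harder to see.

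Renal findings are a natural focus of safety review for this drug class in children, so this is a table people will look at.

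**Working it through.** **Step 1: is there a baseline condition anywhere?** SAP 16.2, SAP 16.2.1 and Protocol 13.1.5 contain none for markedly abnormal values. The treatment-emergent definition in SAP 16.1 covers adverse events only. Appendix 3 builds baseline into four parameters (hemoglobin, hematocrit, red cell count, creatinine) and into no urinalysis item.

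**Step 2: do entry criteria keep children below the limits?** Compare the screening rules with the Appendix 3 flags.

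| Parameter | Entry rule (Protocol 7.1, 7.2) | Appendix 3 flag |
|---|---|---|
| ALT, AST | excluded at ≥2.5 × ULN | >3 × ULN |
| Total bilirubin | excluded at ≥1.5 × ULN (Gilbert exception) | >2 × ULN |
| Albumin | excluded below 2.5 g/dL | <2.5 g/dL |
| Urine protein, blood, casts | no numeric limit; criterion 11 allows stable, explained abnormality | ≥1+, ≥1+, any |
| Urine glucose | no numeric limit; HbA1c >8.5% excluded | ≥1+ |

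For these chemistry items a child at the flag would normally have been screened out. For urinalysis only the severe end is removed: eGFR below 30 mL/min/1.73 m², dialysis, and severe nephrotic syndrome not in remission.

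**Step 3: how large could the effect be?** The documents give no rate of abnormal urinalysis at entry, so there is no plan figure to reproduce. What follows is an illustration.

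Inputs from the documents: 213 randomized (Protocol 8.2) and a 20% secondary-hypertension share (Protocol 6.2.1), so 0.20 × 213 ≈ 43 children.

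Assumptions: 25%, 50% or 75% of those children have protein ≥1+ at entry that persists, and they remain in the study. Then b = 0.20 × 0.25, 0.50 or 0.75 = 5%, 10% or 15% of all children, or about 11, 21 or 32 of 213.

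With i the new-onset rate among children below the limit at baseline:

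printed rate = b + (1 − b) × i

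| b | Printed, i = 2% | Printed, i = 5% | Printed, i = 10% |
|---|---|---|---|
| 5% | 0.05 + 0.95 × 0.02 = 6.9% | 9.8% | 14.5% |
| 10% | 0.10 + 0.90 × 0.02 = 11.8% | 14.5% | 19.0% |
| 15% | 0.15 + 0.85 × 0.02 = 16.7% | 19.3% | 23.5% |

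The pre-existing share of the printed count is b divided by the printed rate. It runs from 34% (b = 5%, i = 10%: 0.05/0.145) to 90% (b = 15%, i = 2%: 0.15/0.167).

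**Step 4: dilution between two arms.** Take true new-onset rates of 10% and 5%, a risk ratio of 2.0, with the same b in each arm:

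- b = 5%: 0.145/0.0975 = 1.49
- b = 10%: 0.190/0.145 = 1.31
- b = 15%: 0.235/0.1925 = 1.22

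**Step 5: which baseline applies?** For laboratory data SAP 16 and Protocol 13.1.5 use the last value before the first DB dose as the baseline for the OL phase. SAP Appendix 1 says Week 8 data, laboratory tests included, serve as the OL baseline. With a Week 8 baseline, an abnormality that arose on AZM before Week 8 would be classed as pre-existing in the OL phase. For the Withdrawal phase SAP 16 uses the last DB value, so an abnormality that arose during the DB phase would likewise drop out of a new-onset count.

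**The case against.** Several points on the other side stand.

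- **Shift tables.** They cover categorical results, so a child abnormal on Day 1 and at Week 6 would appear as unchanged. They use normal ranges, not Appendix 3. The central laboratory's urinalysis ranges are not in the documents, so for dipstick items the two boundaries may nearly coincide. What the shift tables would mainly miss is worsening by grade in a child already positive.
- **The label.** Protocol 13.1.5 describes a plain count and percentage meeting a threshold. On that reading the word incidence is loose and the table is not computed wrongly. The SAP still uses the word, and a reader of the output will take it at face value.
- **Limited reliance.** SAP 16 plans no between-group comparisons of safety data unless a section says otherwise. Adverse event tables are unaffected, because Protocol 10.1.3 does not record pre-existing conditions as events. Creatinine is already judged against baseline.
- **Templates.** SAP 8 refers to table templates that are not in the documents reviewed. A footnote there could already settle the matter, though the rule belongs in the SAP text.

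A reader might also infer three stronger things that the documents do not support. The first is that the table is largely a count of underlying renal disease; that depends wholly on an assumed entry rate. The second is that the count is biased against AZM; randomization balances entry disease in expectation, so the DB effect is dilution. The third is that nothing restrains abnormal urinalysis at entry, or that new cases would be hidden; criterion 11 and the renal exclusions are partial restraints, and shift tables and listings remain.

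**Conclusion.** The point holds as a defect in one safety table. The Appendix 3 urinalysis limits are fixed, entry rules admit children who already exceed them, and no rule separates those children from new cases. Any persistent abnormality at entry therefore raises the printed rate and, in the DB phase, shrinks the relative difference between arms. That direction needs no assumption about frequency.

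The size does. If 5–15% of children enter with persistent protein ≥1+, a 2% new-onset rate prints as about 7–17%, and a true risk ratio of 2.0 (10% against 5%) prints as 1.22–1.49. These figures also assume that the children stay positive and in the study, and that the share is equal across arms. The documents confirm none of this.

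The problem matters most in the OL phase, where no comparator helps the reader. It does not touch efficacy or adverse event reporting. The mismatch between SAP 16.2 and 16.2.1 on the source of the limits, and between SAP 16 and Appendix 1 on the OL baseline, should be resolved whatever the entry rate proves to be.

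**What to change.** 1. **Source of the limits.** In the SAP 16.2 bullet, replace the reference to central laboratory reference ranges with a reference to Appendix 3.
2. **Split by baseline status.** Present the number and percentage of subjects with a post-baseline markedly abnormal value, split by whether the same criterion was met at baseline. Use children below the limit at baseline as the denominator for the new-onset rate. Show baseline-positive children separately, with any worsening by dipstick grade.
3. **DB and OL baseline.** Use the last value before the first DB dose, as SAP 16 states, and correct Appendix 1 so that it no longer calls Week 8 the OL baseline for this purpose.
4. **Withdrawal phase.** Keep the SAP 16 baseline (last DB value), and show abnormalities that arose during the DB phase as a carried-over category so that they do not disappear.

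**Cost.** One baseline flag and some SAP wording. Day 1 urinalysis is already part of the scheduled panel, and every value stays in the listings. The tables become slightly longer, and some cells will be small: 11–32 baseline-positive children over four DB arms is about 3–8 per arm.

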16.2.1. LABORATORY REFERENCE RANGES AND MARKEDLY ABNORMAL CRITERIA

Quantitative laboratory measurements will be compared with the relevant laboratory reference ranges in SI units and categorized as:

- Low: Below the lower limit of the laboratory reference range.
- Normal: Within the laboratory reference range (upper and lower limit included).
- High: Above the upper limit of the laboratory reference range.

Document: 2014-000674-18 Statistical Analysis Plan Version 7.0 Version Number: 7.0

Author: Version Date: 13JAN2020

Template No.: CS_TP_BS016 Revision 5 Reference: CS_WI_BS005

Effective Date: 01Apr2018

In addition to the high and low quantitative laboratory assignments (as identified by means of the laboratory reference ranges), markedly abnormal quantitative safety (and other) laboratory assessments will also be identified in accordance with the predefined markedly abnormal criteria as presented in provided in Appendix 3.

16.3. ECG EVALUATIONS

Results from the central ECG (Electrocardiogram) Reading Centre will be included in the reporting of this study.

The following ECG parameters will be reported for this study:

- PR Interval (msec)
- QRS Interval (msec)
- QT Interval (msec)
- QTc Interval (msec)
- HR (bpm)
- Overall assessment of ECG (Investigator's judgment):
 - o Normal
 - Abnormal, Not Clinically Significant (ANCS)
 - o Abnormal, Clinically Significant (ACS)

Corrected QT interval will be calculated by Arbor or designee and will not be recorded on the CRF. High Low criteria in listing will be derived using table in Appendix 6.

A list of ECG evaluations will be provided as well.

16.4. VITAL SIGNS

The following Vital Signs measurements will be reported for this study:

- Sitting/Standing Systolic Blood Pressure (mmHg)
- Sitting/Standing Diastolic Blood Pressure (mmHg)
- Sitting/Standing Pulse Rate (bpm)

At each visit, three serial sitting BP measurements will be obtained and the average (arithmetic mean) of the 3 serial measurements will be used for the summary.

Descriptive summaries by visit and change from baseline will be provided for vital sign data.

7.0 Document: 2014-000674-18 Statistical Analysis Plan Version 7.0 Version Number: Author: Version Date: 13JAN2020

Template No.: CS_TP_BS016 Revision 5 Reference: CS_WI_BS005

Effective Date: 01Apr2018

16.5. PHYSICAL EXAMINATION

Physical examination data will be listed.

16.6. OTHER SAFETY ASSESSMENTS

The following summaries will be provided for anthropometric data:

- Height z-score
- Weight z-score
- BMI z-score

Height, weight and BMI are collected on the Weight and Height page of eCRF.

Z-score will be calculated using CDC growth charts. The detail is explained in Appendix 4.

Descriptive summaries by visit and change from baseline will be provided for anthropometric data.

Document: 2014-000674-18 Statistical Analysis Plan Version 7.0

Version Number:

Version Date:

13JAN2020

7.0

Template No.: CS_TP_BS016 Revision 5

Reference: CS_WI_BS005

Effective Date: 01Apr2018

Author:

17. REFERENCES

APPENDIX 1. Programming Conventions for Outputs

OUTPUT CONVENTIONS

Outputs will be presented according to the following:

- **Output File Naming Conventions:**
 - File names should only consist of uppercase letters, lowercase letters, digits (0 to 9) and underscores. A period should only be used to indicate a separator between the file name and the extension. No spaces, other special characters or punctuation marks are permitted.
 - As far as possible, output files should be in RTF format, although .DOC files are also permitted.
 - The program, program log and output file name should reflect the type and number of the statistical output. If this is not possible, then the output name should be at least as descriptive as possible. A prefix can be used to distinguish between a Table, Listing and Figure document ('T' for table, 'L' for listing and 'F' for figure). If there is only 1 digit in the number of the table, listing or figure in the place where 2 digits are possible, a leading zero should be added in the file name to make sorting consistent with the sequence (e.g. T14_3_01_1.RTF).
- Paper Size, Orientation and Margins

	Landscape	Portrait
Paper Size	U.S. Letter (8.5 x 11 inch)	U.S. Letter (8.5 x 11 inch)
Margins (Inches):		
Тор	1.25	1
Bottom	1	1
Left	1	1.25
Right	1	1
Header (Inches)	0.5	0.5
Footer (Inches)	0.5	0.5
SAS® Specifications:		
PAGESIZE	46 (8-point size, Courier)	67 (8-point size, Courier)
	41 (9-point size, Courier)	60 (9-point size, Courier)
LINESIZE	134 (8-point size, Courier)	93 (8-point size, Courier)
	119 (9-point size, Courier)	82 (9-point size, Courier)

Fonts

Document: 7.0 2014-000674-18 Statistical Analysis Plan Version 7.0 Version Number: Author: Version Date: 13JAN2020

Template No.: CS_TP_BS016 Revision 5 Reference: CS_WI_BS005

Effective Date: 01Apr2018

- The font type 'Courier New' should be used as a default for tables and listings, with a font size of 8. Single spacing should be used for all text.
- Figures should have a default font of "Courier New".
- This can be achieved by using the following options in SAS®:
- goptions
- gunit = pct
- cback = white
- colors = (black)
- hby = 2.4
- ftext = "TimesRoman"
- htext = 2.5
- device = cgmof97l
- gaccess = gsasfile;
- filename gsasfile "....cgm";
- Spacing:
 - There must be a minimum of 1 blank space between columns (preferably 2).
- Missing values:
 - A "0" should be used to indicate a zero frequency.
 - A blank will be used to indicate missing data in an end-of-text table or patient listing.
 - Figure output conventions:
 - Figures should be provided in RTF files using the SAS® Output Delivery System (ODS), as Computer Graphics Metafile (CGM) formatted graphical output generated by SAS®.
 - The CGM file itself should contain the title or footer.
 - The image should be clear and of high quality when viewed in the Word document, and when printed.
 - In general, boxes around the figures should be used.

DATES & TIMES

Dates will be shown in ddmmmyyyy format, time of day in hh:mm format and datetime values as "ddmmmyyyy; hh:mm". In case of partial dates or time of day, missing information will be replaced by dashes.

SPELLING FORMAT

English US.

PRESENTATION OF TREATMENT GROUPS

For outputs, treatment groups will be represented as follows and in that order:

2014-000674-18 Statistical Analysis Plan Version 7.0 7.0 Document: Version Number: 13JAN2020 Author: Version Date:

Template No.: CS_TP_BS016 Revision 5 Reference: CS_WI_BS005

Effective Date: 01Apr2018

Phase	Treatment Group	For Tables and Graphs
Double Blind Phase	Losartan	Losartan
	AZM low	AZM-L
	AZM Intermediate	AZM-M
	AZM High	AZM-H
Withdrawal Phase	Placebo	Placebo
	Losartan	Losartan
	AZM low	AZM-L
	AZM Intermediate	AZM-M
	AZM High	AZM-H
Open Label Phase	AZM Only	AZM Only
	AZM plus additional	AZM Plus
	antihypertensives	

PRESENTATION OF VISITS

For outputs visits will be represented as follows and in that order:

Long Name (default)	Short Name
Screening /Visit 1	Scr /V1
Washout/Placebo Run-In /Visit 2	PRI /V2
D-1/ Visit 3	D-1 /V3
D1/ Visit 4	D1 /V4
Week 2 / Visit 5	W2 / V5
Week 4 / Visit 6	W4 / V6
Week6 – 1D / Visit 7	W6-1D / V7
Week 6 / Visit 8	W6 / V8
Week 8 / Visit 9	W8 / V9
Week 12 / Visit 10	W12 / V10
Week 20 / Visit 11	W20 / V11
Week 28 / Visit 12	W28 / V12
Week 36 / Visit 13	W36 / V13
Week 44 / Visit 14	W44 / V14
Week 52 – 1D /Visit 15	W 52 –1D / V15
Week 52 /Visit 16	W52 / V16
Week 54 /Visit 17	W54 / V17

DEFINITION OF PHASES AND TREATMENT ASSIGNMENT:

Visit4/D1 - Visit 8/W6 = Double Blind Phase Visit 8/W6 - Visit9/W8 = Withdrawal Phase

Document: 2014-000674-18 Statistical Analysis Plan Version 7.0 Version Number: 7.0 Author: Version Date: 13JAN2020

Template No.: CS_TP_BS016 Revision 5 Reference: CS_WI_BS005

Effective Date: 01Apr2018

Visit9/W8 - Visit16/W52 = Open Label Phase

All the data collected for procedures (Con Meds, Vital Signs, AE assessments, Laboratory tests, Pregnancy tests) at Visit 8/ W6 will be used as visit 8/W6/last visit of DB phase in DB analysis and as WD phase baseline in WD phase analysis because all the measurements are taken before WD phase drug is given to the subjects at Visit 8/W6.

All the data collected for procedure (Con Meds, Vital Signs, Physical Examination, AE assessments, Laboratory tests, Pregnancy tests, ECG) at Visit9/ W8 will be used as visit 9/W8/last visit of WD Phase in WD phase analysis and OL baseline in OL analysis because all the measurements are taken before OL drug is given to the subjects at Visit 9/ W8.

Visit 4/Day 1 - First day of Double-Blind Dose Visit 8/Week 6 - First day of Withdrawal Phase Dose Visit 9/Week 8 – First day of Open Label Dose

LISTINGS

All listings will be ordered by the following (unless otherwise indicated in the template):

- Site-subject ID,
- Randomized treatment group (or treatment received if it's a safety output), first by active dose [by ascending dose group] and then control/placebo
- Phase
- Visit
- Date (where applicable),
- For listings where non-randomized subjects are included, these will appear in a category after the randomized treatment groups labelled 'Not Randomized'.

GENERAL DISPLAY

When a table/listing is split in multiple pages, the footnotes added to explain the table/listing should be displayed on each page of the table/listing and not only on the last one.

Document: 2014-000674-18 Statistical Analysis Plan Version 7.0

Version Number:

Version Date: 13JAN2020

7.0

Template No.: CS_TP_BS016 Revision 5 Reference: CS_WI_BS005

Effective Date: 01Apr2018

Author:

